#### Statistical analysis

A Shapiro-Wilk's test was used to determine normal distribution of the data. Independent t-tests were used for evaluating baseline characteristics at the BE and placebo visits. Dependent variables were assessed using a  $2 \times 2$  repeated measures analysis of variance (ANOVA) [group (BE and placebo)  $\times$  time (before and after supplement intake)] to determine differences between pre- and post-BE and placebo intake. If a significant effect was noted, paired t-tests were used for post hoc comparisons. All statistical analyses were performed with SPSS 26.0 (IBM, Armonk, NY). Data are presented as Mean  $\pm$  SD unless noted otherwise. Statistical significance was set to  $p < 0.05$ . It was calculated that a minimum of 16 total participants in a crossover design (16 each group, BE and placebo) would enable 80% power to observe a 3 to 5% change in FMD between the two groups. An effect size analysis was performed using Cohen's d and interpreted 0.2, 0.5, and 0.8 as small, medium, and large effect sizes, respectively.

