## Study protocol

### Participants

Healthy adults (n = 18, age 19-35, 9 males and 9 females) who were recreationally active volunteered to participate in this study. Exclusion criteria included 1) any cardiovascular, neurological, metabolic, respiratory, or renal diseases, 2) any musculoskeletal conditions or injuries, 3) presence or history of stomach ulcers, 4) prescribed medications or over-the-counter medications, 5) pregnant, trying to become pregnant, or breast-feeding women, 6) any history of smoking/current smoker, and 7) any allergies to fruits or vegetables. The procedures used in this study were approved by the Institutional Review Board at the University of Nebraska Medical Center and carried out in accordance with the Declaration of Helsinki. All participants gave their written informed consent prior to study enrollment, during which the experimental procedures, potential risks, and potential benefits were explained. This study was registered with <https://clinicaltrials.gov/> (NCT04312022).

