### Study design

A randomized, double-blind, placebo-controlled, crossover study design with a 2-week washout period was used. After study enrollment, participants were randomly assigned to either the BE supplement group or the placebo control group. All data collections were performed at the same time of day ( $\pm 1\text{h}$ ) after an overnight fast, and participants were asked to abstain from caffeine, alcohol, high intake of antioxidant-rich foods or supplements, and excessive exercise for at least 48 hours prior to their visits. Participants were also informed to not change their dietary habits during the study period. Descriptive measurements of height, weight, BMI, body composition, and hand grip strength were taken at both BE and placebo visits. Baseline measurements of RHR, BP, blood sampling for TAC, endothelial function, skeletal muscle oxygen utility capacity during exercise, and muscular fatigue index were assessed. Participants then consumed either the BE or placebo, and all baseline measures were repeated as experimental measures 1 hour after BE or placebo intake. A 1-hour digestion period was chosen because anthocyanins have been shown to reach peak levels in the blood within 1-hour post consumption. After 2 weeks each participant returned for a second visit and the same protocol was repeated with the intervention (BE or placebo) they did not receive in the first visit. All women (n = 9) were tested during the early-to-mid follicular (days 1 – 10) and late-luteal phases (> day 19) of the menstrual cycle in order to avoid confounding effects of endogenous estrogen on autonomic function.

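### Baseline values from the BE and placebo visits are compared with independent t-tests although the same 18 people supply both sets

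*Combined protocol and SAP*

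**What the plan says.** The Statistical analysis section of the combined protocol and SAP gives the baseline comparison in one sentence: "Independent t-tests were used for evaluating baseline characteristics at the BE and placebo visits".

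The Participants section describes a single cohort: "Healthy adults (n = 18, age 19-35, 9 males and 9 females". The Study design section makes it a two-period crossover, in which "each participant returned for a second visit and the same protocol was repeated with the intervention (BE or placebo) they did not receive" at the first visit. The same section states: "Descriptive measurements of height, weight, BMI, body composition, and hand grip strength were taken at both BE and placebo visits".

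Elsewhere the Statistical analysis section respects the within-person structure. Outcomes go into a 2 × 2 repeated measures ANOVA (group by time), and "If a significant effect was noted, paired t-tests were used for post hoc comparisons".

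The plan gives no between-visit correlation for any measure. It does not say how the baseline test result will be read, and it attaches no decision to it.

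**The concern.** An independent t-test assumes two unrelated samples. Here each person contributes one value to each side, so the test treats 18 pairs as 36 different people. When a person's two values are positively correlated, much of the between-person variation cancels in the within-person difference. The independent test leaves that variation in the error term, so its standard error is too large and it rejects too rarely. The plan also treats the same pairing in two ways within one section, without giving a reason.

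What is at stake is the statement that the two visits began from similar baselines. A test with little power for small-to-moderate differences makes that statement look better supported than it is.

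**Working it through.** **Inputs from the documents.** 18 participants, each at both visits (Participants; Study design); independent t-test for baseline (Statistical analysis); significance level 0.05 (same section).

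**Assumptions.** Two-sided testing (sidedness is not stated); equal SD at the two visits, set to 1; normally distributed values; r over a range, because the documents give none. The plan states no figure for this comparison, so there is none to reproduce.

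**Standard error of the mean difference between visits, in SD units.**

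- Independent test: √(2/18) = 0.333, whatever r is.
- Correct value for paired data: √(2(1−r)/18).
- Ratio: 1/√(1−r).

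**Critical values.** 2.032 on 34 degrees of freedom (independent) and 2.110 on 17 (paired).

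**Half-width of the 95% interval.** Independent: 2.032 × 0.333 = 0.68 SD at every r. Paired: 2.110 × √(2(1−r)/18), for example 2.110 × √(1/18) = 0.50 SD at r = 0.5.

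**Rejection rates.** Independent test by simulation of 18 correlated normal pairs (at least 500,000 datasets per setting); paired test from the noncentral t distribution.

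| Assumed r | SE overstated by | False-positive rate, independent | Power for 0.5 SD shift, independent | Power for 0.5 SD shift, paired | Half-width, paired (SD) |
|---|---|---|---|---|---|
| 0 | 1.0 | 5.0% | 31% | 29% | 0.70 |
| 0.3 | 1.2 | 2.1% | 28% | 39% | 0.59 |
| 0.5 | 1.4 | 0.8% | 25% | 52% | 0.50 |
| 0.8 | 2.2 | 0.02% | 18% | 88% | 0.31 |
| 0.9 | 3.2 | below 0.01% | 13% | 99% | 0.22 |

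The paired test keeps a 5% false-positive rate at every r.

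**Large shifts.** The independent test still finds them. For a 1 SD shift its power is 90% at r = 0.5 and 96% at r = 0.8. For a 0.8 SD shift it is 70% and 76%.

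**The same effect on a single p-value.** With equal visit SDs, t(paired) = t(independent)/√(1−r), where r is the sample correlation. An independent-test p of 0.20 on 34 degrees of freedom is t = 1.307.

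- At r = 0.5: 1.307/0.707 = 1.848, which on 17 degrees of freedom gives p = 0.082.
- At r = 0.8: 1.307/0.447 = 2.922, which gives p = 0.0095.

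**Where the direction reverses.** The paired test has fewer degrees of freedom. At the 0.05 boundary the independent p-value becomes the larger one only when 1 − r < (2.032/2.110)², that is, when r exceeds about 0.07.

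**Effect on the supplement comparison.** The group-by-time contrast is (post − pre at the BE visit) − (post − pre at the placebo visit). A shift s added to both values at one visit gives (post + s) − (pre + s) = post − pre, so it drops out.

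**The case against.** The strongest reply concerns weight. No conclusion about the supplement rests on this test: the outcome analysis is within-person and uses each visit's own pre-intake value. The plan nowhere says that a non-significant baseline result will be taken as equality, and a non-significant paired test would not prove equality either. The striking contrasts need a high r and a 0.5 SD mean shift together, and a shift of that size in height or BMI over two weeks, in adults told to keep their diet unchanged, is hard to credit. The term used for the baseline variables may also cover only the descriptive measures and not the pre-intake outcome values, which Study design lists separately.

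Most of this stands as a limit on severity. The figures are illustrative, and the caution about reading non-significance as equality applies to any such test. None of it justifies the independent test: under either reading of the term, the values come from the same 18 people. The implausibility argument is also weaker for grip strength, which depends on effort on the day, and for the pre-intake outcome values if they are included.

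**Conclusion.** The concern holds, as a minor point. The stated test does not match the design, and no other part of the plan repairs it. For any correlation above about 0.07 its p-values near the 0.05 boundary are too large. With r between 0.5 and 0.9, the chance of detecting a 0.5 SD difference between visits falls from 52–99% (paired) to 25–13% (independent), while shifts of about 0.8 to 1 SD are still usually found. These sizes rest on assumed r, assumed shifts and equal visit SDs; the fact of the pairing rests on the documents alone. The consequence is confined to what can be said about baseline comparability. The group-by-time test is not directly affected.

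**What to change.** Replace the baseline sentence with one to this effect: *each baseline measure will be compared between the two visits within person, using a paired t-test, and reported as the mean within-person difference with its 95% confidence interval.* State which variables the comparison covers. Judge comparability from the size of the difference and its interval, not from a non-significant p-value.

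The cost is one sentence and a re-run of the baseline table from data already collected. If r were near zero the paired test would be very slightly less powerful (29% against 31% for a 0.5 SD shift). The change does not separate a period effect from a difference between the BE and placebo visits.

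### The crossover ANOVA has no period (sequence) term; it is valid on average, but a sequence-adjusted sensitivity estimate and the sequence counts would be a cheap improvement

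*Combined protocol and SAP*

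**What the plan says.** Under Study design, "participants were randomly assigned to either the BE supplement group or the placebo control group". Because the trial is a crossover, this fixes the order of the two treatments. Each visit has its own pre-dose and post-dose measurements: "all baseline measures were repeated as experimental measures 1 hour after BE or placebo intake". Then, "After 2 weeks each participant returned for a second visit and the same protocol was repeated", with the other capsule. The allocation ratio, any blocking and the number who took each order are not given.

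Under Statistical analysis, the dependent variables go into a 2 × 2 "repeated measures analysis of variance (ANOVA) [group (BE and placebo" by time, "to determine differences between pre- and post-BE and placebo intake". Follow-up is described in one sentence: "If a significant effect was noted, paired t-tests were used for post hoc comparisons". No period, sequence or visit-order term appears. The sample size is "a minimum of 16 total participants in a crossover design", stated to give 80% power for a 3 to 5% difference in FMD; 18 took part.

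**The concern.** In a two-period crossover the randomised groups are the two sequences, and a standard analysis uses them to separate treatment from visit order. This model does not. If the one-hour change tends to differ between visit 1 and visit 2 whatever capsule is taken, that difference enters the treatment contrast with opposite signs in the two sequences. With equal sequences it cancels from the estimate but stays in the error term. With unequal sequences part of it also stays in the estimate. With 18 participants, either could matter. The stated model can neither detect nor remove it, and without the sequence counts a reader cannot tell which case applies.

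**Working it through.** **Inputs.** From the documents: n = 18 (Participants); planned minimum 16, 80% power, significance at 0.05 (Statistical analysis). Assumed: two-sided testing; both ANOVA factors within participant, which the crossover implies but the text does not state; a range for the period effect p; and, where noted, simple 1:1 randomisation.

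**The plan's own figure.** No SD is given, so 16 cannot be reproduced. For a paired t-test at n = 16, 80% power corresponds to an effect of 0.749 SD of the paired difference. A 3% difference then implies an SD of 3/0.749 = 4.0, and 5% implies 5/0.749 = 6.7. The same effect has 85% power at n = 18. The results below use the effect with 80% power at n = 18, which is 0.70 SD of D.

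**What the test is.** For each participant, D = (BE post − BE pre) − (placebo post − placebo pre). The group-by-time interaction is the one-sample t-test on D with 17 df. Adding a constant to both measurements of a visit leaves D unchanged. A period effect p on the change adds +p to D in one sequence and −p in the other.

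**Bias given the split.** The mean of D moves by p(n1 − n2)/18: 0 at 9:9, 2p/18 = 0.11p at 10:8, 4p/18 = 0.22p at 11:7, 6p/18 = 0.33p at 12:6. With p = 0.5 SD of D, the bias at 12:6 is 0.167 SD, or 0.167/0.70 = 24% of the powered effect. At 10:8 it is 0.056 SD, or 8%.

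**Where type I error passes 5%.** The unmodelled ±p also inflates the estimated variance. With d = n1 − n2, the squared bias is p²d²/324, and the added variance estimate for the mean is p²(18 − d²/18)/(17 × 18). These are equal at d² = 18, so d = 4.24. At 11:7, d = 4, just below; at 12:6, d = 6, above. Simulation agrees (p in SD of D; last column from the noncentral t with 16 df):

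| Split | Type I error, p = 0.35 | Type I error, p = 0.5 | Power of sequence-adjusted test if p = 0 (ANOVA 80%) |
|---|---|---|---|
| 9:9 | 3.8% | 2.9% | 79.7% |
| 10:8 | 4.1% | 3.4% | 79.2% |
| 11:7 | 4.9% | 4.7% | 77.7% |
| 12:6 | 6.2% | 6.9% | 74.9% |

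The sequence-adjusted test holds about 5% throughout. Under simple randomisation of 18, 12:6 or worse has probability 23.8% and 10:8 or closer 51.9%. Averaged over simple randomisation, the unadjusted type I error is 5.0 to 5.1% for p from 0 to 1 SD of D.

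**Power at 9:9.** For p = 0.2, 0.35 and 0.5 SD of D, the ANOVA has about 79%, 76% and 72%; the sequence-adjusted test stays at 80%. At 12:6 with p = 0.35, the ANOVA has 88% if the period effect adds to the treatment effect and 60% if it opposes it, against 75% adjusted.

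**Cost averaged over simple randomisation.** ANOVA against sequence-adjusted power: 80.0 and 77.3% with no period effect; 78.5 and 77.2% at p = 0.2; 77.6 and 77.2% at 0.25; 76.5 and 77.3% at 0.3. Adjustment gains power only above about p = 0.27 SD of D, which is 0.27/0.70 = 39% of the treatment effect.

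**Pre-dose covariate.** Let rho be the correlation between the pre-dose and post-dose BE-minus-placebo differences (unknown). Sequence plus the pre-dose difference (15 df) at 9:9 with no period effect has power of about 87%, 83%, 81% and 79% at rho 0.5, 0.7, 0.8 and 0.9.

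**The case against.** The strongest reply is that the plan is valid as written. Averaged over randomisation it is unbiased with a 5% error rate, whole-visit shifts cancel, and nothing in the documents shows a period effect on the one-hour change. Visits are at the same time of day, fasted, after 48 hours of abstention, with familiarisation for the leg tests. Large losses need large effects: ANOVA power at 9:9 falls to 61% only at p = 0.79 SD of D, more than the 0.70 SD treatment effect itself. If allocation was blocked, 12:6 is practically excluded; if it was simple, adjustment costs about 3 power points on average when there is no period effect. All of this stands, and it limits the point to a minor improvement. It does not remove it: the sequence counts would show whether bias can arise, and the adjusted estimate needs no new data.

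Three stronger readings are tempting and unsupported.

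- A reader might infer that menstrual phase creates the period effect, because women "were tested during the early-to-mid follicular" and late-luteal windows with visits two weeks apart. That requires a 28-day cycle, an exact 14-day gap, most women starting in the same phase, and phase altering the pre-to-post change. None of these is stated, so this is speculation.
- A reader might infer that the change score misuses the pre-dose value. It is a valid choice; a covariate only affects precision.
- A reader might infer that whole-visit shifts contaminate the post hoc t-tests. That holds only if these compare BE with placebo on post-dose values. The text does not say so, and pre versus post within a condition is equally possible.

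**Conclusion.** The concern holds as a minor point. The stated ANOVA omits the sequence term; it is not an invalid test. A period effect on the change would make it conservative and less powerful at 9:9 (a loss of about 1 to 8 power points for p of 0.2 to 0.5 SD of D). At any unequal split it would bias the estimate, given that split, in proportion to the imbalance. It would be wrong to say that bias begins at 12:6; that is where type I error first exceeds 5%. It would also be wrong to conclude that the trial's error rate is inflated, since neither the split nor a period effect is documented. The figures rest on assumed period effects, two-sided testing, within-participant factors and, for the averaged results, simple randomisation.

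**What to change.** Report the allocation method and the number of participants in each sequence, state that both ANOVA factors are within participant, and say which pairs the post hoc t-tests compare.

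Beside the stated ANOVA, regress D on sequence (coded +1/−1), one row per participant. The intercept is the BE-minus-placebo effect, with 16 df; give it with its 95% CI. Do this first for FMD, the outcome on which the sample size is based, and then for the other outcomes. The text is in the past tense and Blood sampling reports assay coefficients of variation, so data apparently exist. If they have already been analysed, label the result a sensitivity analysis and keep the stated ANOVA. The adjustment does not address carryover.

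Optionally, regress the post-dose difference on sequence and the pre-dose difference (15 df), reported separately so that the precision gain is not confused with the period adjustment.

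Cost: wording and one ordinary regression per outcome in the software already used. With no period effect, the sequence term costs under 1 power point at 9:9 or 10:8, about 2 at 11:7, about 5 at 12:6, and about 3 averaged over simple randomisation. At 9:9 the covariate version ranges from a gain of about 7 points (rho 0.5) to a loss of about 1 (rho 0.9), relative to 80%.

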#### Skeletal muscle oxygen utility capacity

Skeletal muscle oxygen utility capacity during single leg extension exercise was assessed before and after BE and placebo intake. Oxygenation utility capacity of the vastus lateralis was measured during leg extension exercise with a commercially available NIRS system (Artinis PortaMon, Einsteinweg, The Netherlands). The PortaMon emits near-infrared wavelengths of 850 and 764 nm and has a detection probe to measure returning signals, and data were recorded continuously at 10 Hz to quantify tissue saturation index (StO2, %) and concentrations of both oxygenated hemoglobin ([O2Hb], a.u.) and deoxygenated hemoglobin ([HHb], a.u.).

To determine single leg extension strength, a 1-repetition maximum (1RM) test was performed using the participant's dominant leg. Participants were familiarized with the leg extension technique before the 1RM measurement, which was achieved within 3 attempts. The 1RM was considered the highest weight that could be lifted in good form through a full range of motion. The PortaMon was secured with a commercially available, double-sided adhesive at one- third of the distance from the lateral femoral epicondyle and the greater trochanter, and the device was adjusted to be on the belly of the vastus lateralis muscle. The device was wrapped in black, light-absorbing cloth to reduce extraneous light that may affect the signals. Participants were then asked to perform 15 repetitions at 60% of their 1RM while NIRS data were recorded continuously throughout the exercise protocol.

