#### Fatigability index

Fatigability index was quantified during Isokinetic contraction of the participant's dominant leg before and after BE and placebo intake using HUMAC NORM Isokinetic Dynamometer (CSMi Solutions, Stoughton, MA). The participants were seated upright with the axis of rotation of the dynamometer arm oriented with the axis of rotation of the participant's dominant knee. Belts and straps were used to secure the participant to the dynamometer, and participants were instructed to fully extend and flex their knee and to work to their maximal capacity during the leg extension exercise. Before the test, there were 4 familiarization repetitions at the testing resistance. The testing consisted of a mild resistance at 240°/sec to induce and measure muscular fatigue. The software (HUMAC 2015, v.15.000.0103) reported the data of fatigue index, which was calculated using the percentage peak torque differences that were

found on the first and final 5 repetitions of the exercise bout (fatigue index = [initial peak torque – final peak torque]/initial peak torque \* 100). The data obtained from the analysis software allowed for the assessment of changes in numbers relative to the participant baseline measurements.

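### The post hoc rule does not require a significant group × time interaction, so a time effect shared by BE and placebo can open within-condition tests that may be read as a supplement effect

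*Combined protocol and SAP*

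**What the plan says.** The Statistical analysis section specifies a 2 × 2 repeated measures ANOVA with factors group (BE, placebo) and time (before, after intake). Its stated purpose is "to determine differences between pre- and post-BE and placebo intake". The follow-up rule is: "If a significant effect was noted, paired t-tests were used for post hoc comparisons". Neither the triggering effect nor the pairs are named there or anywhere else in the document.

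Three other statements bear on the reading:

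- The sample-size sentence is about a between-condition difference: 16 participants "would enable 80% power to observe a 3 to 5% change in FMD between the two groups".
- Under Study design, "all baseline measures were repeated as experimental measures 1 hour after BE or placebo intake", and the same is done at both visits. This includes the loaded leg extension ("Skeletal muscle oxygen utility capacity during single leg extension exercise was assessed before and after BE and placebo intake") and the isokinetic bout, in which participants were told "to work to their maximal capacity during the leg extension exercise".
- Under Fatigability index, the dynamometer data are said to have "allowed for the assessment of changes in numbers relative to the participant baseline measurements".

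**The concern.** The ANOVA yields three tests per outcome: group, time and group × time. The time effect averages the pre-post change over both conditions and says nothing about BE against placebo. The interaction alone tests whether the BE change differs from the placebo change.

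A shared time effect is plausible in this design, most directly for the leg-muscle outcomes, because the same exercise is done twice about an hour apart at each visit. Fatigue, warm-up or practice could move both conditions together, and the placebo visit exists to remove that movement. If the shared shift opens the follow-up tests, and a significant pre-post test after BE is then read as a supplement effect, the claim no longer rests on the placebo comparison and its error rate is not the nominal 5%. The apparent effect would take the direction of the shared shift, so it could look like benefit or harm.

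Both conditions are needed for that harm: the shared effect has to trigger the tests, and the within-condition result has to be read as evidence for BE.

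**Working it through.** **The plan's own figure.** The only figure nearby is the minimum of 16 participants for 80% power. The documents give no SD or within-person correlation, so it cannot be reproduced. Working backwards with a two-sided 5% paired t-test, n = 16 requires a standardised paired difference of 0.75. If the 3 to 5% is taken as FMD percentage points, the implied SD of the paired difference is 3/0.749 = 4.0 points or 5/0.749 = 6.7 points. That is attainable, and this point does not depend on it.

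**Inputs.** From the documents: n = 18 and significance at p < 0.05 (taken as two-sided, since sidedness is not stated). Assumed: error SD 1 per measurement; the same true shift δ at both visits (no BE effect); correlation ρ of 0 to 0.75 between a person's two change scores.

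**Formulas.** The SD of a change score is √(1 + 1) = √2. Each test has 17 df and critical value 2.11.

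- BE pre-post test: noncentrality √18 × δ/√2 = 3δ.
- Time effect (mean of the two changes, SD √(1 + ρ)): noncentrality √18 × δ/√(1 + ρ).
- Interaction (BE change minus placebo change): noncentrality 0 for every δ.

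At δ = 0.7 and ρ = 0.5, the BE test has noncentrality 2.1 and the time test 4.243 × 0.7/1.225 = 2.42. By the noncentral t distribution, the time effect is significant in about 63% of trials (about 80% at ρ = 0). The interaction stays at 5%.

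**Simulation.** 200,000 trials per setting. The table gives the percentage of trials in which at least one of the three ANOVA effects is significant, the BE pre-post test is significant and the placebo pre-post test is not:

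| Shared shift δ (error SD) | 0 | 0.25 | 0.5 | 0.7 | 1.0 | 1.25 | 1.5 |
|---|---|---|---|---|---|---|---|
| ρ = 0 | 2.9 | 6.9 | 17.6 | 23.1 | 15.4 | 5.5 | 1.1 |
| ρ = 0.5 | 2.5 | 5.1 | 11.1 | 14.1 | 10.1 | 4.1 | 1.0 |
| ρ = 0.75 | 1.9 | 3.7 | 7.3 | 9.0 | 6.7 | 2.8 | 0.7 |

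- **Interaction required first:** the BE-only pattern never exceeds 2.3% (ρ = 0, δ = 0.7).
- **Source of the excess:** BE-only patterns that arise without a significant time effect make up at most 1.5% of trials.
- **Conflict with the interaction:** at δ = 0.7, the interaction is not significant in 20.8/23.1 = 90% of BE-only patterns (ρ = 0) and in 12.2/14.1 = 87% (ρ = 0.5).
- **BE significant whatever placebo does:** about 26% of trials at δ = 0.5 and 48% at δ = 0.7.

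**Cross-check on another scale.** A separate simulation expressed the shift in SDs of the change score and used ρ of 0 or 0.3. Its 0.5 corresponds to 0.5 × √2 = 0.71 error SD here. With n = 18, time was significant in 70–81% of trials and the interaction in 5%. The BE pre-post test was significant in about 49–50% and BE only in 18–23%. Requiring the interaction cut the last two to about 2.6% and 2.1–2.3%. The two sets agree.

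**The case against.** The strongest reply is that this is an under-specified sentence and not a stated wrong rule. The harm requires that a time effect alone counts, that the pairs are pre against post within a condition, that BE significant with placebo not significant is read as efficacy, and that a moderate shared shift exists. The documents state none of these. If the pairs were BE against placebo at each time, a shared shift would not produce the error. The group × time model and the sample-size sentence both point to a between-condition question, and a change from own baseline is also the raw material of the interaction contrast.

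Much of this stands as a limit. The percentages are illustrative. They peak near 0.7 SD, are smaller at high correlation, and fall below 5% with no shift or a very large one. Placebo-only patterns are equally frequent, by symmetry. The fatigue-index sentence is weak evidence for either reading.

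It does not remove the problem. The ANOVA's stated purpose concerns pre-intake against post-intake differences, so within-condition pairs are the natural reading, and nothing in the text excludes a time effect as the trigger. An analyst who follows the sentence literally can reach a wrong conclusion. One who already meant the interaction loses nothing by saying so.

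**Conclusion.** The concern holds. The rule as written lets a time effect shared by both conditions open the paired tests, and no other part of the document restricts it to the interaction. With 18 participants and no BE effect, a misleading BE-only result arises in about 7–18% of trials at a shared shift of 0.5 error SD and 9–23% at 0.7 SD, over correlations 0.75 to 0. With the interaction required, it is at most about 2%.

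That the omission is there is certain. Its consequence is conditional on the assumed shift and correlation, on within-condition pairs, and on those results being read as evidence for BE. The document does not say that such a claim was or would be made; it permits it.

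**What to change.** Replace the follow-up sentence with wording such as: *The BE effect is judged only by the group × time contrast (BE change minus placebo change), reported with its 95% CI. Paired post hoc comparisons are made only if that contrast is significant; the pairs are listed in advance, and within-condition pre-post tests are descriptive.*

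The interaction is already part of the planned ANOVA, so no new data or model is needed. The price is fewer nominally significant within-condition results to claim. The section is written in the past tense. If the analysis is already done, the authors should state which effect triggered the paired tests and which pairs were compared, and report the interaction estimate with its CI as the test of BE. In that case the change clarifies or relabels results and cannot count as pre-specification. The 5% level of the interaction test is per outcome. No multiplicity adjustment across outcomes is stated, and this fix does not supply one.
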